## 5.1 EFFICACY ASSESSMENTS

### 5.1.1 RECIST v1.1

The primary efficacy endpoint, ORR, will be evaluated using RECIST v1.1 ([Eisenhauer, 2009](#)) as described in [Appendix C](#) (For patients with bone-exclusive disease, the modified MDA bone criteria will be used to assess response; see [Table 11](#) for response criteria for bone metastases). A repeat of tumor imaging will be required for the purposes of confirmation of response (i.e., partial response, and/or complete response). The confirmation scan should be no earlier than 4 weeks following the first indication of response.

In addition to local imaging assessments performed by the Investigator, scans will be sent to central imaging for possible future reads.

The central imaging read is being conducted for regulatory purposes only. The Investigator is responsible for diagnostic and treatment decisions concerning their patients.

The process for image collection and transmission to the ICR during the study can be found in the Imaging Manual.

Disease staging will be collected at diagnosis and Screening for this protocol, prior to any treatment initiation. The minimum duration of stable disease will be defined as  $\geq 4$  weeks in determining the best overall response. To document evidence of prior disease progression, tumor measures prior to baseline assessments may be requested by the Sponsor.

The imaging requirements are provided in [Table 2](#).

Confidential

Document State: Effective (Controlled)  
CONFIDENTIAL

Page 41 of 118

**Table 2** **Imaging Guidelines**

Study Period	Schedule	Imaging (RECIST 1.1)	Imaging (MDA)
Screening	Within 28 days prior to day 1	
At screening, the following image scans are required:
 
 
1. MRI of brain
 
2. CT of Neck
 
3. CT of Chest
 
4. CT of Abdomen and
 
5. CT of Pelvis
 
	
For bone disease only patients, the following anatomic regions on MRI are required at ALL timepoints to assess osseous metastatic burden:
 
 
1. Skull (usually included in MR Brain)
 
2. Cervical Spine
 
3. Thoracic Spine
 
4. Lumbar Spine
 
5. Pelvis
 
6. Rib Cage (shoulders to be in field of view)
 

Treatment	Every 8 weeks ( $\pm$ 3 days) until disease progression	
Follow up scans at 8-week intervals, the following image scans are required:
 
 
1. MRI of the brain for known or suspected disease
 
2. CT of Neck
 
3. CT of Chest
 
4. CT of Abdomen
 
5. CT of Pelvis required for known or suspected disease in the abdomen to ensure complete anatomic coverage of tumor burden. CT of the pelvis is preferred if there is suspected disease in the pelvis
 
	Same as screening visit
End of Study (EOS) Visit	30 days post last investigational product ( $\pm$ 7 days)	
At EOS the following image scans are required:
 
 
1. MRI of the brain for known or suspected disease
 
2. CT of Neck
 
3. CT of Chest
 
4. CT of Abdomen
 
5. CT of Pelvis required for known or suspected disease in the abdomen to ensure complete anatomic coverage of tumor burden. CT of the pelvis is preferred if there is suspected disease in the pelvis
 
	Same as screening visit

Confidential

 Document State: Effective (Controlled)  
 CONFIDENTIAL

Page 42 of 118

Study Period	Schedule	Imaging (RECIST 1.1)	Imaging (MDA)
Long-Term Follow-up	Every 3 months ( $\pm$ 7 days)	
At Long-Term Follow-up the following image scans are required:
 
 
1. MRI of the brain for known or suspected disease
 
2. CT of Neck
 
3. CT of Chest
 
4. CT of Abdomen
 
5. CT of Pelvis required for known or suspected disease in the abdomen to ensure complete anatomic coverage of tumor burden. CT of the pelvis is preferred if there is suspected disease in the pelvis
 
	
Confirmation of Response Scan	The confirmation scan should be no earlier than 4 weeks following first indication of response (PR or CR)	
For confirmation no earlier than 4 weeks following a PR or CR, the following are required:
 
 
1. MRI of the brain for known or suspected disease
 
2. CT of Neck
 
3. CT of Chest
 
4. CT of Abdomen
 
5. CT of Pelvis required for known or suspected disease in the abdomen to ensure complete anatomic coverage of tumor burden. CT of the pelvis is preferred if there is suspected disease in the pelvis
 
	Same as screening visit

Confidential

 Document State: Effective (Controlled)  
 CONFIDENTIAL

Page 43 of 118

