### **Prior/Concomitant Therapy**

7. Completed palliative radiation therapy  $<$  7 days prior to initiating investigational product.

Confidential

Document State: Effective (Controlled)  
CONFIDENTIAL

Page 37 of 118

8. Prior treatment with gamma secretase inhibitors. Prior treatment with anti-Notch antibodies may be allowed upon discussion with the Sponsor's medical monitor.
9. Last chemotherapy, biologic, or investigational therapy agent <4 weeks or 5 half-lives (whichever is shorter) prior to initiating investigational product; 6 weeks if the last regimen included BCNU or mitomycin C. Prior treatment with investigational monoclonal antibody will be reviewed case-by-case by the Sponsor.

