### **5 STUDY PROCEDURES**

- Study procedures and their timing are summarized in SoA in Table 1.
- No protocol-related procedures should be performed before patients provide written informed consent.
- Procedures conducted as part of the patient's routine clinical management and obtained before signing of the ICF may be utilized for screening or baseline purposes provided the procedures met the protocol-specified criteria and were performed within the time frame defined in the SoA.
- Study-related events and activities including specific instructions, procedures, concomitant medications, dispensing of investigational products, and descriptions of AEs should be recorded in the appropriate source documents and eCRF.
- Immediate safety concerns should be discussed with the Sponsor immediately upon occurrence or awareness to determine if the patients should continue or discontinue study intervention.
- Adherence to the study design requirements, including those specified in the SoA, is essential and required for study conduct.

Confidential

Document State: Effective (Controlled)  
CONFIDENTIAL

Page 40 of 118

- All screening evaluations must be completed and reviewed to confirm that potential patients meet all eligibility criteria. The investigator will maintain a screening log to record details of all participants screened and to confirm eligibility or record reasons for screening failure, as applicable.
- For patients who discontinue study therapy early for the reasons specified in Section [4.5](#), an End of Study (EOS) visit will be conducted as specified in SoA (Table 1). Other procedures and evaluations will be completed as deemed necessary by the Investigator.
- For the long-term overall survival status assessment, patients and/or their caregivers will be contacted by phone every 3 months after EOS visit until death, patient withdraws consent or Sponsor terminates the study.
- An unscheduled visit may be performed throughout the study at the patient's request or as deemed necessary by the Investigator. The date and reason for the unscheduled visit will be recorded. The Investigator will monitor AEs and record concomitant medications. Other procedures and evaluations will be completed as the Investigator deems necessary; they may include (but are not limited to) safety laboratory tests, ECG, vital signs and physical examination.

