#### 7.1.4 Prohibited Concomitant Medication

Medications specifically prohibited in the exclusion criteria are not allowed during the ongoing study. If there is a clinical indication for any medication or vaccination specifically prohibited during the study, discontinuation from study therapy or vaccination may be required. The Investigator should discuss any questions regarding this with the Sponsor's Medical Monitor. The final decision on any supportive therapy or vaccination rests with the Investigator and/or the patient's primary care physician. However, the decision to continue the patient on study therapy or vaccination schedule requires the mutual agreement of the Investigator, the Sponsor and the patient.

Patients are prohibited from receiving the following therapies during the Screening and Treatment periods (including retreatment for post-complete response relapse) of this study:

- Prior treatment with gamma secretase inhibitors.
- Note: the following situations are considered 1 line of therapy:
  - *Discontinuation of one drug in a multi-drug regimen and continuation of (an) other drug(s).*
  - *Restarting the same regimen after a drug holiday.*
  - *Switching from IV to oral formulation of the same drug is also considered one regimen.*

Confidential

Document State: Effective (Controlled)  
CONFIDENTIAL

Page 66 of 118

- Exposure to any investigational drug within 4 weeks or 5 half-lives whichever is longer or concurrently with investigational product administration.
- Chronic systemic glucocorticoid use (high dose defined as > 10 mg/day prednisone or equivalent).
- Use of any herbal supplements within 1 week prior to investigational product administration.
- Use of medications causing Torsades de Pointes within 1 week or 5 half-lives (whichever is longer; see [Appendix A](#)).
- Use of strong inhibitors of CYP3A4 within 1 week or 5 half-lives (whichever is longer) or strong inducers of CYP3A4 within 2 weeks or 5 half-lives (whichever is longer; see [Appendix B](#)).
- At least 6 months must have elapsed after prior therapy with any investigational nucleoside analogue.

Patients who, in the assessment by the Investigator, require the use of any of the aforementioned treatments for clinical management should be removed from the study. Patients may receive other medications that the Investigator deems to be medically necessary.

The Exclusion Criteria describes other medications that are prohibited in this study.

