#### **Target Lesions:**

- Identify a maximum of 5 **target lesions** (up to 2 target lesions per organ).
  - Target lesions must be **measurable**; where measurable is defined:
    - 10 mm in the longest diameter by CT (preferred) or MRI scan (or no less than double the slice thickness) for non-nodal lesions and  $\geq 15$  mm in short axis for nodal lesions
    - 10 mm caliper measurement by clinical exam
    - 20 mm by chest X-ray
- **NOTE:** Regardless of the imaging modality blastic bone lesions will not be selected as target lesions. Lytic or mixed lytic-blastic lesions with a measurable soft tissue component  $\geq 10$  mm can be selected as target lesions.
- **NOTE:** Lesions having undergone prior intervention (e.g., previous irradiation) will not be selected as target lesions unless there has been a demonstration of progress in the lesion.
- Target lesions should be selected on the basis of their size (lesions with the longest diameter), be representative of all involved organs, but in addition should be those that lend themselves to reproducible repeated measurements.
- Calculate the **sum of the diameters (SOD)** of all target lesions.
  - For non-nodal lesions: the longest diameter should be included in the sum of diameters
  - For nodal lesions: the short axis measurement (i.e., widest dimension perpendicular to the long axis) should be included in the sum of diameters

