#### Target Lesions:

Target lesions are measured at every subsequent assessment and an overall SOD is calculated. Target lesions are assessed as Complete Response (CR), Partial Response (PR), Stable Disease (SD), Progressive Disease (PD), or Not All Evaluated (NAE) at every time point based on the calculated SOD.

Target Assessment	Evaluation Definition
Complete Response (CR)	CR is declared if ALL of the following are true for target lesions: 
 
• The disappearance of all non-nodal target lesions
 
• Any pathological lymph nodes must have a reduction in short axis to <10 mm.
 

Partial Response (PR)	PR is declared if there is a decrease of at least 30% in the SOD of target lesions compared to the baseline SOD of target lesions.
Progressive Disease (PD)	PD is declared if ANY of the following are true for target lesions: 
 
• SOD of all target lesions increases at least 20% compared to the smallest SOD recorded from any prior assessment
 
 NOTE: In addition to the relative increase at least 20%, the sum must also demonstrate an absolute increase of at least 5 mm. 
OR
 
 
• The appearance of one or more new lesions.
 

Stable Disease (SD)	SD is declared if target lesion assessment does not meet criteria for PR, PD, or CR.

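### The baseline scan need not follow the end of earlier treatment, so shrinkage from a prior drug or palliative radiation can occasionally be counted as a confirmed AL101 response

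*Protocol*

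**What the plan says.** **Baseline scan.** The Screening row of Protocol Table 2 sets the window as "Within 28 days prior to day 1". Section 5 lets routine-care procedures "obtained before signing of the ICF may be utilized for screening or baseline purposes" if they meet the protocol's criteria and fall in the scheduled time frame. Neither place links the scan to the end of earlier treatment.

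**Prior drugs.** Exclusion 9 in Protocol Section 4.2 excludes "Last chemotherapy, biologic, or investigational therapy agent <4 weeks or 5 half-lives (whichever is shorter) prior to initiating investigational product", with 6 weeks for BCNU or mitomycin C. Section 7.1.4 prohibits "Exposure to any investigational drug within 4 weeks or 5 half-lives whichever is longer or concurrently with investigational product administration".

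**Prior radiation.** Exclusion 7 applies to patients who "Completed palliative radiation therapy" less than "7 days prior to initiating investigational product". Section 7.1.3 permits limited-field palliative radiation during study participation, with prior Medical Monitor approval and not to the only measurable or assessable site. Section 3 counts screening as part of participation.

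**Response.** Appendix C says "Lesions having undergone prior intervention (e.g., previous irradiation) will not be selected as target lesions" unless they have progressed. It also says "PR is declared if there is a decrease of at least 30% in the SOD of target lesions compared to the baseline SOD". Best overall response counts from the first dose to the next anticancer therapy, and a CR or PR must be confirmed at least 4 weeks later (Protocol Section 9.6.1, SAP Section 6.4.1.1).

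**The concern.** PR is measured against the baseline sum, so anything that shrinks a target lesion between the baseline scan and the first on-treatment scan is credited to AL101. The scan window reaches back 28 days, while the permitted end of earlier treatment can lie within days of Day 1. Treatment can therefore be given after the scan that serves as the reference. The rule for best overall response deals with therapy given after AL101, not with therapy given just before it.

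The sequence is foreseeable. Pre-screening may take place while the patient is on other therapy, and Section 7.1.3 names painful bone metastases as an occasion for radiation. Appendix C acts when targets are chosen, so it does not reach a lesion that is chosen first and irradiated later. Table 11, used for bone-exclusive disease, has no rule on irradiated lesions.

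At stake is the primary endpoint. The trial is non-comparative, so no concurrent arm would show the same carry-over, and the null response rate is only 8%.

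**Working it through.** **1. Time windows (from the documents).**
- Earliest baseline scan: Day -28.
- Drug: five half-lives are shorter than 28 days when the half-life is below 28 / 5 = 5.6 days. The documents name no specific prior drug, so half-lives are assumed: 6, 12, 24 and 48 hours give washouts of 1.25, 2.5, 5 and 10 days. Prior dosing could then follow a Day -28 scan for up to 26.75, 25.5, 23 and 18 days.
- Radiation: up to 28 - 7 = 21 days after a Day -28 scan.
- With a Day -28 scan and the first on-treatment scan at week 8, 28 / (28 + 56) = 33% of the interval precedes AL101.

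**2. What one irradiated lesion can do (illustration).** Targets of 40, 20 and 15 mm sum to 75 mm. If the 40 mm lesion falls to 15 mm and the others do not change, the sum is 50 mm and the decrease is (75 - 50) / 75 = 33.3%, which meets PR. This needs a 25 / 40 = 62.5% reduction in that lesion, still present at confirmation. A single lesion can do this alone only if it makes up at least 30% of the baseline sum.

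**3. The plan's own operating characteristics.** The Cohort 2 design is n = 42, look at 21, r1 = 2, r2 = 6, 8% against 25%. Stopping at 2 or fewer of 21 and claiming success at 7 or more of 42, exact binomial sums give power 88.6% (stated: 89.4%) and type I error 3.95%. SAP Section 7.9 says that the Cohort 2 futility analysis was not conducted. The rule in practice is then 7 or more of 42, with type I error 4.7% and power 92.9%. The documents give no cut-off for Cohort 1. I use 8 or more of 45, the smallest count that keeps the error at 5% or below (2.5%; 7 or more gives 6.5%).

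**4. Effect of spurious responses (assumed rates).** If a fraction q of non-responders is scored as responders because of earlier treatment, the null rate becomes p = 0.08 + 0.92q. The error is the binomial probability of reaching the cut-off at p.

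| q (assumed) | p | 7 or more of 42 | same, with look at 21 | 8 or more of 45 |
|---|---|---|---|---|
| 0 | 8.0% | 4.7% | 3.95% | 2.5% |
| 1% | 8.9% | 7.6% | 6.4% | 4.4% |
| 2% | 9.8% | 11.4% | 9.6% | 7.0% |
| 3% | 10.8% | 16.0% | 13.6% | 10.5% |
| 5% | 12.6% | 27.4% | 23.6% | 20.0% |

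In patients, 42 x 0.92 x q is 0.4, 0.8 or 1.2 extra responders expected at q = 1%, 2% or 3%. About one patient is enough to matter.

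**The case against.** Several safeguards exist, and they carry weight.

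- **Confirmation.** A response first seen at week 8 must still be present at about week 12. A short half-life drug, already stopped for five half-lives at Day 1, would have to leave a lasting shrinkage of at least 30%. That makes the drug route uncommon. It does little against lasting shrinkage of an irradiated lesion.
- **Radiation controls.** Radiation during screening needs Medical Monitor approval and may not go to the only measurable site. One of several targets may still be treated.
- **Entry progression.** Progression within 6 months of consent, or newly diagnosed metastatic disease, is required. It need not be progression on the last therapy.
- **SAP subgroups.** Response rate is shown by prior radiation, systemic therapy and chemotherapy. The groups without such treatment are free of that carry-over, but the split does not identify treatment given after the scan.
- **Testing.** The primary analysis is an estimate with a Clopper-Pearson interval, and the protocol makes testing conditional. The upward shift in the estimate is the same either way.
- **Imaging Manual.** It is not among the documents and may contain a timing rule.

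Three stronger readings are not supported. A reader might infer that carry-over routinely produces responses; the documents show only that it can. A reader might infer that an old scan turns earlier treatment into false progression. Growth before Day 1 is not caused by earlier treatment, and with assumed volume doubling times of 60 to 180 days the sum of diameters grows 3.7% to 11.4% in 28 days, below the 20% threshold. A reader might infer that hormonal agents have no washout; Section 7.1.3 sets one for anti-androgens.

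**Conclusion.** The gap is real and limited. Following the protocol as written, a patient can receive a prior drug or palliative radiation after the baseline scan, and the resulting shrinkage can count as a confirmed AL101 response. The visible text neither prevents this nor removes such patients from any analysis of response rate.

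Its size cannot be found from the documents, which give no carry-over rate. The 1% to 3% range is an assumption: it takes the type I error to between 7.6% and 16.0% in Cohort 2 without the look, and to between 4.4% and 10.5% in Cohort 1. At 1%, Cohort 1 stays below 5%. These figures show how little room an 8% null leaves; they are not an estimate of what happened.

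Separately, exclusion 9 takes the shorter of 4 weeks and five half-lives for investigational agents, while Section 7.1.4 takes the longer. Both cannot apply to the same drug.

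**What to change.** - **Protocol Table 2 and Schedule of Activities footnote m:** state that the baseline scan is taken within 28 days of Day 1 and after both the last dose of prior anticancer drug and any palliative radiation, and is repeated before Day 1 if it was not. SAP Section 7.1.3 takes the last measurement before first infusion as baseline, so a repeat scan would become the reference.
- **Appendix C, including Table 11:** state that a lesion irradiated after the baseline scan is not used as a target for response.
- **SAP Section 7.5.2:** flag patients whose prior therapy or radiation ended after the baseline scan, and add one row for the response rate with their responses counted as non-responses.
- **Exclusion 9 and Section 7.1.4:** reconcile the two washout statements. No washout is proposed here.

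The cost is a slightly tighter screening timetable, an occasional repeat scan and one extra analysis row. SAP Section 4 describes an update between dry run and database lock, so the scan rule cannot help patients already treated. The sensitivity row still can. It uses mainly data already collected: SAP Section 7.4.4 summarizes prior treatment and time since last radiation. Availability of stop dates for prior systemic therapy should be checked, because that section does not list them.

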### **5.1.2 Patient Reported Outcome: European Organization for Research and Treatment of Cancer Quality of Life Questionnaire 30 questions (EORTC QLQ-C30)**

The EORTC QLQ-C30 will be administered during the study at screening and then every 4 weeks before investigational product administration.

EORTC QLQ-C30 was developed as an instrument to measure cancer patients' physical, psychological and social functions (Kaasa, 1995). The questionnaire is composed of 5 multiitem scales (physical, role, social, emotional and cognitive functioning) and 9 single items (pain, fatigue, financial impact, appetite loss, nausea/vomiting, diarrhea, constipation, sleep disturbance and quality of life) (Kyriaki, 2001). It is validated and reliable and has been used successfully in various types of cancer, including head and neck cancer (Bjordal, 2000; Chaukar, 2005).

The example of the English version of the EORTC QLQ-C30 can be found at [Appendix D](#) and at this link:

<https://www.eortc.org/app/uploads/sites/2/2018/08/Specimen-QLQ-C30-English.pdf>

## **5.2 SAFETY ASSESSMENTS**

Planned time points for all safety assessments are provided in the SoA ([Table 1](#)).

### **5.2.1 Adverse Events**

Adverse events (AEs) will be assessed and recorded at all study visits throughout the study from informed consent signing through EOS visit (30 days following cessation of investigational product) (see Section [8.1](#)).

### **5.2.2 Adverse Events of Special Interest**

Adverse event of special interest (AESI) will be assessed and recorded at all study visits throughout the study from baseline through EOS visit (30 days following cessation of investigational product). For details see Section [8.4](#).

### **5.2.3 Medical History and Concomitant Medications**

Any clinically significant diseases in the prior 3 years including any co-morbid conditions requiring active treatment as well as significant surgeries will be documented in the medical history section of the eCRF. This includes prior medical history and treatment regimen for ACC.

Abnormal physical examination finding and/or the diagnosis of concomitant disease resulting from assessment at Screening must also be documented in the medical history section.

Information on all interventions (systemic therapy, surgery, radiation treatment) related to the patient's cancer will also be collected. Radiology and photography reports from imaging conducted as routine care will be collected if available from the last 3 years.

Concomitant medication is defined as any prescription or over-the-counter preparation, including vitamins and supplements. Use of concomitant medication from 28 days before Day 1 of Cycle 1 through 30 days after the last dose of investigational product must be recorded onto the eCRF

Confidential

Document State: Effective (Controlled)  
CONFIDENTIAL

Page 44 of 118

from the patient's medical file. This will include trade name or generic name, strength, unit, route of administration, dosage form, frequency, indication, start and stop date(s) of administration. Refer to Section [7.1](#) for prohibited and allowed medications.

